2. STUDY DESIGN

An analytical, longitudinal, experimental, prospective, controlled and randomized clinical study will be conducted to analyze the cause-effect relationship of the Müller & Puig physiotherapy protocol under study in relation to the change in pain, functionality (modified Harris scale) and the range of mobility (ROM) in subjects surgically operated by Femoro-acetabular Impingement (FAI) by arthroscopy.

The study will be simple blind with blinded evaluator strategy with two parallel groups. The surgeons (recruitment) and assessors will be blinded with respect to the group belonging to the subject. The statistician will be blinded to the subjects group until the statistical analysis is completed. It is not possible to blind the physiotherapist who executes the treatment protocol or the study subjects. Subjects will be asked not to disclose their membership group or consult with the surgeon or the evaluator.

The randomization approach will be prepared by means of a randomization computer program, attributing a 1:1 ratio to the membership group. The interventionist physiotherapist will perform the randomization on the day of the first post-surgery physiotherapy session.

All participants will be informed of the purpose of the study through an information document prepared for this purpose and will be clarified any doubts that may arise. After answering as many questions as necessary, the subject must sign the informed consent document to be part of the study. The principles of the Declaration of Helsinki (2004) will

be respected at all times. The data collected will be treated confidentially by applying the current legislation on the protection of personal data (Organic Law 15/1999 of December 13, Protection of Personal Data) and / or any other applicable.

This study has been admitted by the Research and Ethics Committee of General University Hospital of Elche PI 6/2019.

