5. STUDY VARIABLES

5.1. Independent variables study object

The independent variables of the project are: a) belonging to the control or intervention group; and b) time, according to the timing of presurgical and postsurgical measurements. We also recorded as independent variables the general characteristics of the sample: age, BMI, sex, hours of weekly sports activity, orthopedic surgeon who performed the intervention and compliance with the program.

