The sample will be divided into 2 groups: Intervention Group and Control Group. The postoperative physiotherapeutic treatment protocol described will be applied to the intervention group. The non-intervention group will receive the nonspecific protocol of postoperative treatment for hip rehabilitation described by Gocen et al.

7. EVALUATION.

The evaluator is the person who will perform the pre and postsurgical measurements. He will be trained in the use of the goniometer and in the performance of orthopedic tests as well as in the material to be used. It will be located in the "Evaluation Room", with the material and conditions necessary to carry out the measurements. It will register and store the data for its later evaluation and statistical analysis.

The evaluator will be blinded with respect to the subject's belonging to the intervention or control group.

Data will be recorded at three times: before surgery, after 4 weeks and after 14 weeks of surgery. Immediate postoperative measurements will not be made, given that the clinical picture and tissue injury of the intervention could cause inaccurate results because a period of post-surgical wound stabilization has not elapsed.

These tests and measurements of variables will provide us with the degree of hip readjustment and its functionality, since they respond to the affected musculoskeletal structures both prior to the arthroscopy intervention due to the pathophysiology of the FAI, and after it for the wounds and surgical scars that are generated.

8. STUDY SEQUENCE.

A. Recruitment: it takes place before the surgery in the Traumatology clinic of Alicante Clinic (we attach authorization of the center to carry out the study) Two facultative specialists in orthopedic surgery and traumatology, transfer the information to the patient in written support about the characteristics of the study , purpose and form of follow-up, at the same time that they verify the eligibility of the subject according to the criteria of the study. Another member of the research team will independently check the eligibility of the subject in an evaluation session and will be responsible for performing the evaluations of the study variables before surgery, at 4 and 14 weeks after surgery. The evaluator will be present to resolve and clarify any doubts in this regard. After this, and with the acceptance of the patient to be part of the study, the informed consent will be signed.

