B. Pre-surgery evaluation: the Harris scale questionnaire modified prior to the surgical procedure will be completed. After signing the informed consent, the pre-surgical measurement will be carried out following the following sequence:

- Assessment tests of abduction, adduction, flexion, extension, internal rotation and external rotation ROM of the hip
- Next, the Ober, Fabere and Faddir muscle tests will be performed.
- Finally, the pain will be evaluated through the Visual Analog Scale (VAS)

C. Randomization: After the presurgical evaluation and following a simple randomization process by means of a computer program, the subjects are assigned to the control or intervention group.

D. Hip arthroscopy: The study subjects will receive adequate pre- and postoperative care including health education and exercise plan for the immediate postoperative period, in addition to a follow-up visit by the traumatologist after two weeks of the intervention.

E. Intervention: The subjects of the control group follow the general postsurgical treatment protocol described by Gocen et al. The subjects of the intervention group will perform a physiotherapy session of 45 minutes each one every two weeks for a total of 7 sessions (weeks 2, 4, 6, 8, 10, 12 and 14 post surgery) following the protocol described. In addition, they will have to follow a physiotherapy exercise plan at home whose compliance they will have to register in an activity diary to check adherence to treatment.

F. Post-surgery evaluation 1: The evaluation described in section B and C is repeated 4 weeks after surgery to subjects of both groups.

G. Post-surgery evaluation 2: The evaluation described in section B and C is repeated after 14 weeks of the surgery for the subjects of both groups, and the individual study is finished.

In both groups, it will be advised to avoid stairs, ramps, squats, forced hip flexion and legs crossing in all phases. The subjects that develop a deterioration in the Modified Harris scale or in the VAS at 4 weeks after surgery compared with the pre-surgical data or those subjects that reflect complications of the surgery will be evaluated again by their corresponding traumatologist to decide whether or not to remain in the program. All complications will be documented by the principal investigator. No adverse effects are expected.

Statistical Analysis Plan (SAP)

Size Sample and Feasibility

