The statistical program that we will use will be SPSS v.20. To determine the sample size, a pilot study will be conducted with the same methodology as the original study to a group of 10 subjects. These subjects will be assigned to the same group. This pilot study will provide us with the estimates of the mean and variance of the response variable, thus being able to calculate the appropriate sample size by determining a minimum power value of 80% ($W > 80\%$) and a confidence level of 95% ($p < 0.05$).

The pilot sample will be part of the final sample to be studied if there are no changes in the protocol or in the variables to be measured.

The FAI is an important cause of coxarthrosis. Hip osteoarthritis is a pathology of high prevalence, with important socioeconomic repercussions. In Spain, 16% of the population over 20 years of age suffers, with a clear prevalence in women.

In a retrospective radiological study, Marín et al found around 70% the presence, on radiographs performed years before the intervention, of femoral and acetabular signs suggestive of femoroacetabular shock in children under 55 years who underwent total arthroplasty of hip. Other authors have reported values around 45% in patients pending intervention of hip prostheses with an age range between 30 and 82 years.

We consider it feasible to obtain a sample necessary for the present study (around 30 subjects per group) in view of the sample size of published articles on the effectiveness of conservative or postoperative treatment protocols for hip disorders and FAI and the high prevalence of FAI. The estimated time of obtaining the necessary sample will be around 6 months.

Descriptive analysis: A descriptive statistical analysis of all the variables will be carried out using frequency tables for the qualitative variables, and the minimum, maximum, average and standard deviation for the quantitative variables.

Inferential analysis: In relation to the inferential analysis, the statistical tests described below will be performed.

- a. Normal distribution test of Kolmogorov-Smirnov to identify the distribution of the samples.
- b. Levene test to check if the variances are homogeneous.

- c. ANOVA test (when the sample were are normal) or Kruskal-Wallis test (when it do not comply with normality) to check the homogeneity of the characteristics of the subjects between the different groups before the intervention.

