- d. For the comparison of means between the results of both groups we will use the t-Student test of related samples and one-way ANOVA (when they are normal) or Mann-Whitney U test or Wilcoxon W test (when they do not meet the normal).
- e. Chi square test or ANCOVA to analyze the influence of the general characteristics of the sample on the effect of the intervention.
- f. For the reliability analysis of the measuring tools, Cronbach's alpha test will be used.
- g. Regression analysis using the multiple linear model to study the relationship between sets of variables.

A significance index of $p < 0.05$ will be established.

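### Simple randomisation leaves operating surgeon and arm sizes to chance, and the main group comparison has no surgeon term: a small, cheaply avoided loss of precision

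*Combined protocol and SAP*

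**What the plan says.** **Allocation.** Section 8C describes "following a simple randomization process by means of a computer program, the subjects are assigned to the control or intervention group". Section 2 adds only "attributing a 1:1 ratio to the membership group", and gives the task of randomising to the physiotherapist who delivers the treatment. Neither place mentions blocks, strata or minimisation.

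**Surgeon.** Section 5.1 ends its list of general sample characteristics with "orthopedic surgeon who performed the intervention and compliance with the program". Section 8A has "Two facultative specialists in orthopedic surgery and traumatology" informing patients and checking eligibility. The number of surgeons who operate is not stated.

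**Size.** The SAP expects "around 30 subjects per group", given as a feasibility figure.

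**Analysis.** SAP item c tests whether the groups are alike at baseline. Item d compares the groups with t, one-way ANOVA or rank tests and names no covariate. Item e proposes chi-square or ANCOVA for how the sample's general characteristics influence the intervention effect. Item g proposes a multiple linear model without naming its variables.

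**The concern.** Every follow-up outcome is measured after surgery, at 4 or 14 weeks. If surgeons' results differ, surgeon is a source of outcome variation. The plan records the variable but uses it neither in allocation nor in the main comparison. Two things follow. In the single randomisation that this trial will have, one arm may by chance hold noticeably more of one surgeon's patients. And between-surgeon variation stays in the error term of item d, which lowers power. Item c does not help, because a test of baseline homogeneity adjusts nothing. Simple randomisation also fixes the 1:1 ratio only in expectation, so the arms may differ in size.

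**Working it through.** **Inputs from the documents:** simple 1:1 allocation (sections 2 and 8C); about 30 per group, taken as 60 in total (SAP, sample size); power target from "determining a minimum power value of 80" per cent; "A significance index of $p < 0.05$ will be established", taken as two-sided. The plan's size cannot be reproduced, because no effect size or SD is given.

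**Assumptions:** all 60 patients are randomised (this sets aside the 10 pilot subjects, whom the SAP places in one group and may retain); two operating surgeons; caseload splits of 30/30, 40/20 and 42/18; a surgeon gap g of 0 to 0.8 within-surgeon SD.

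**1. Arm sizes.** With X ~ Binomial(60, 0.5):
- P(X = 30) = 0.103
- P(25:35 or worse) = 0.245
- P(22:38 or worse) = 0.052

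**2. Power cost of unequal arms.** The effect detectable with 80% power at 30:30 is d = (1.96 + 0.84) × √(2/30) ≈ 0.72 SD. Using Φ(d/√(1/n₁ + 1/n₂) − 1.96):
- 30:30 gives 80.0%
- 25:35 gives 78.9%
- 22:38 gives 77.0%

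Averaged over the binomial distribution, power is 79.3%, a loss of about 0.7 points.

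**3. Surgeon mix.** If a of surgeon A's patients and b of surgeon B's fall in arm 1, the gap in surgeon A's share is a/(a+b) − (n_A − a)/(60 − a − b). The probability that its absolute value is 0.20 or more is:

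| Caseload | Probability |
|---|---|
| 30/30 | 15.5% |
| 40/20 | 12.1% |
| 42/18 | 10.0% |

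A 20-point gap moves the unadjusted group difference by 0.20 × g: 0.06 SD at g = 0.3, 0.10 at 0.5 and 0.16 at 0.8. The standard error of the difference at 30:30 is √(2/30) = 0.26 SD, so these are about 0.2, 0.4 and 0.6 standard errors. The direction is random, and the shift averages zero over randomisations.

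**4. Precision.** With a 30/30 caseload and surgeon left out, the outcome SD is √(1 + g²/4), so surgeon's share of the variance is (g²/4)/(1 + g²/4). Adjusted power at 30:30 is 80.0% throughout.

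| g | Variance share | Unadjusted power, 30:30 | Unadjusted power, simple randomisation | Total gain (points) |
|---|---|---|---|---|
| 0 | 0% | 80.0% | 79.3% | 0.7 |
| 0.3 | 2.2% | 79.1% | 78.4% | 1.6 |
| 0.5 | 5.9% | 77.6% | 76.9% | 3.1 |
| 0.8 | 13.8% | 73.9% | 73.2% | 6.8 |

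This ignores the degree of freedom spent on surgeon and any imbalance from incomplete blocks, both small.

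**5. False positives.** Simulated simple randomisation of 60 patients with no treatment effect and an unadjusted t test gave a rejection rate of about 5% at every surgeon gap tried, up to 0.8 SD.

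**The case against.** The other side has a strong case, and much of it stands.

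- **Simple randomisation is valid.** Chance imbalance in surgeon is part of the sampling error that the test already allows for, as step 5 confirms. A reader might infer that an excess of one surgeon's patients in one arm makes the comparison biased or the p-value wrong. The documents do not support that: the shift in step 3 applies only to an unlucky draw.
- **Item e reaches surgeon.** A reader might also infer that the analysis ignores surgeon altogether. It does not: item e covers the general characteristics, and section 5.1 counts surgeon among them. But item e asks how those characteristics influence the effect, offers chi-square or ANCOVA as alternatives, and fixes neither outcome nor model. The specific objective in section 1 omits surgeon, and item g names no variables. Nothing commits the sponsor to a surgeon-adjusted estimate in the main comparison.
- **The size rests on assumptions.** The documents give no between-surgeon difference and no caseload split. Section 8A counts recruiters, not operators. That more than one surgeon operates is an inference, supported by surgeon being a recorded variable and by section 8's reference to each patient's own traumatologist.
- **Around 30 per group is not a promise of equal arms**, so simple randomisation does not contradict it.
- **Blocking has a price.** The person who randomises is unblinded and learns each allocation. Small blocks within surgeon make later assignments easier to guess. This stands, and the fix has to deal with it.

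**Conclusion.** The point holds as a precision and design-quality matter. Allocation is unstratified, the operating surgeon is recorded, and item d does not use it. The exposure is a surgeon-share gap of 20 points or more in about 10% to 15% of randomisations. Changing both allocation and model would recover roughly 1 to 7 power points, depending on an assumed surgeon gap of 0 to 0.8 SD. Equalising the arms accounts for only about 0.7 of those points; at the upper end most of the gain comes from the model term. The figures assume 60 randomised patients, two operating surgeons and two-sided 5% testing. If only one surgeon operates, only the arm-size part remains. The plan is not invalid as it stands, and the change is optional rather than essential.

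**What to change.** In sections 2 and 8C, replace simple randomisation with permuted blocks of randomly varying size, stratified by operating surgeon. Conceal the list and the block sizes from the physiotherapist who randomises, and reveal one assignment at a time. State how many surgeons operate. In SAP item d, make surgeon a pre-specified factor in the main between-group model, and leave item e for the separate question of influence on the effect.

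The cost is a setting in the randomisation program, an amended sentence in each place, a concealment step that the documents do not now describe, and one degree of freedom per additional surgeon. Allocation becomes slightly more predictable than under simple randomisation; varying the block sizes and hiding the list keep that small. No extra patients or measurements are needed, because surgeon is already recorded.

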1. OBJECTIVES

The objectives of our study are the following:

General:

- Determine the effectiveness of a protocolized treatment of specific physiotherapy for patients undergoing femoroacetabular syndrome by means of arthroscopy in pain, range of mobility and functionality.

Specific:

- Check how the age, level of physical activity prior to the study, sex, level of adherence to the program or body mass index of the subject influences the effectiveness of protocolized treatment of physiotherapy in patients surgically operated on femoroacetabular syndrome by arthroscopy.

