- Standing patient, hip extension with knee in full extension with resistance in the ankle with an elastic band of 1.5 m in length and medium resistance (4 sets of 10 repetitions twice a day)
- Standing patient, hip extension with knee in flexion of 45° with resistance in the ankle with an elastic band of 1.5 m in length and medium resistance (4 sets of 10 repetitions twice a day)
- Standing patient, hip extension with knee in 90° flexion with resistance in the ankle with an elastic band of 1.5 m in length and medium resistance (4 sets of 10 repetitions twice a day)
- Patient sitting and full knee extension with resistance in the ankle with an elastic band of 1.5 m in length and medium resistance (4 sets of 15 repetitions twice a day).
- Basic stretching of quadriceps, hamstrings, adductor and abductor (3 times a week).

Avoid climbing stairs, ramps, squats, forced hip flexion and crossing legs in all phases.

To check the adherence to the treatment, measures based on self-report of the subject

will be used since they are the easiest to obtain and the most frequently used to measure the adherence. The measuring instrument used will be the completion of a diary design for this purpose. It will be used to monitor the performance and duration of the protocol exercises. Through the data obtained in this diary, the overall percentage of therapeutic adherence on the recommended behavior will be determined. This system acts as a reminder increasing the probability of compliance with the work plan.

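### Compliance is listed for the whole sample and sent to the two-arm effect analysis, but the only adherence diary is described for the intervention arm, so that analysis cannot show whether adherence modifies the treatment effect

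*Combined protocol and SAP*

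**What the plan says.** - Section 1 (specific objective) names adherence with age, prior activity, sex and BMI. It asks how "level of adherence to the program or body mass index of the subject influences the effectiveness of protocolized treatment of physiotherapy".
- Section 5.1 lists the recorded characteristics of the sample without limiting any of them to one arm. The list ends with "orthopedic surgeon who performed the intervention and compliance with the program".
- SAP, inferential analysis, item e, plans a "Chi square test or ANCOVA to analyze the influence of the general characteristics of the sample on the effect of the intervention". It gives no model terms, no coding and no rule for missing values.
- SAP item g adds a multiple linear regression, also without stated terms.
- Section 4, which describes the intervention, defines the measure: "The measuring instrument used will be the completion of a diary design for this purpose". From the diary, "the overall percentage of therapeutic adherence on the recommended behavior will be determined". The section adds: "This system acts as a reminder increasing the probability of compliance with the work plan".
- Section 8, item E, describes the two arms in turn. Controls follow the cited general programme. Intervention subjects attend seven sessions, and then: "In addition, they will have to follow a physiotherapy exercise plan at home whose compliance they will have to register in an activity diary". The word 'they' refers to the intervention group.
- Section 7 sets outcome assessments before surgery and at 4 and 14 weeks after it.

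**The concern.** Item e takes up the same set of characteristics that section 5.1 defines, so compliance falls within it. Whether a factor modifies a treatment effect is a comparison between arms, and it needs the factor to be observed in both. As described, adherence is observed in one.

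Two further features separate compliance from the baseline factors beside it. It arises after randomisation, so it can be a result of how well the patient recovers. It is also reduced to one overall percentage, while outcomes are taken at two post-surgical visits.

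The risk is that an association seen only among treated patients, which recovery alone could produce, is reported as adherence changing how well the protocol works.

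**Working it through.** The plan gives no figure for adherence to reproduce. The one relevant figure is the feasibility size of around 30 per group (SAP, sample size), taken here as 30 + 30 = 60.

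**1. The sections side by side.** Section 5.1 implies compliance data for everyone. Sections 4 and 8E describe the instrument only for the intervention arm. No section gives controls a diary, and none says that they lack one. Either 5.1 is too broad or 8E is incomplete.

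**2. What item e can estimate if controls have no diary.** Let G be arm (1 = intervention) and A adherence. Effect modification is b3 in

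Y = b0 + b1·G + b2·A + b3·G·A.

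- *Controls missing and dropped:* G = 1 throughout, so G repeats the intercept and G·A repeats A. Rank is 2 of 4. All controls, about 30 of 60 subjects, are lost, and so is the arm effect.
- *Controls coded 0:* G·A equals A for every subject. Rank is 3 of 4, and b2 and b3 cannot be separated. If the interaction is left out, b2 is only the slope within the intervention arm, and b1 compares a patient with zero adherence with the average control, which is not the treatment effect.
- *Adherence recorded in both arms:* rank is 4 of 4. The term can be computed, but A would then measure adherence to two different programmes and would still be a post-randomisation variable.

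The documents do not say which coding would be used; the first two are the obvious ways to run item e on one-arm data.

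**3. What a within-arm association would show.** Inputs: n = 30 and two-sided 5% (sidedness is assumed, as the SAP does not state it). By Fisher's z, the chance of significance is P(Z > 1.96 − atanh(r)·√27), with √27 = 5.196.

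| assumed r | atanh(r)·√27 | chance of p < 0.05 |
|---|---|---|
| 0.2 | 1.05 | 18% |
| 0.3 | 1.61 | 36% |
| 0.4 | 2.20 | 60% |
| 0.5 | 2.85 | 81% |

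If prognosis correlates 0.4 with adherence and 0.5 with outcome, and adherence does nothing, then r = 0.4 × 0.5 = 0.20. A simulation of that case was significant in about 18% of trials, in line with the first row. The smallest correlation detectable with 80% power is tanh((1.96 + 0.84)/5.196) = 0.49.

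These are powers for assumed correlations. They show how easily recovery alone could yield a significant result. They do not measure the defect, and the fix does not change them.

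**4. Timing.** Section 4 runs from day 1 to day 97, and the 4-week visit falls at about day 28. If the diary covers the whole programme, 97 − 28 = 69 of 97 days (69/97 = 71%) lie after that visit. An overall percentage set against the 4-week outcome would rest mostly on later behaviour. The plan does not say that it will be used in this way, nor that it will not.

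**The case against.** The strongest reply is that the objective concerns adherence to the protocolized programme, which only the intervention arm receives. A within-arm relation between adherence and outcome can be estimated from the diary as planned, and item g could carry it. A complier-type (instrumental-variable) analysis also needs adherence only in the treated arm, provided that controls have no access to the programme and randomisation acts only through it. This stands. A reader might infer that the adherence aim cannot be answered at all, and the documents do not support that. What fails is the moderator analysis under item e. The SAP specifies neither alternative.

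It can also be said that the lack of control data is inferred from silence. That stands too: section 5.1 points the other way, and section 4 speaks of the subject without naming an arm. An empty control column is the natural reading of 8E, not an established fact. Under either reading the text needs an edit.

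A reader might also infer that the one-arm diary biases the trial, since the plan itself credits it with raising compliance. The documents do not support this. The diary is described within the intervention, like the seven sessions, and the comparator is usual guidance. Read as part of the package, it limits how far a difference can be credited to the exercises themselves, but it does not invalidate the comparison.

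Finally, a control diary might seem to be the remedy. In the simulation above, with diaries in both arms, the interaction test was significant in about 4% of trials, close to nominal. That assumed the same relation between adherence and prognosis in both arms, which two different programmes give no reason to expect.

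**Conclusion.** The point holds in a limited form. Sections 4, 5.1, 8E and SAP item e do not fit together. If controls keep no diary, the two-arm analysis of compliance either loses about 30 of 60 subjects, all of them controls, or confounds compliance with arm; in neither case can effect modification be estimated. If controls do keep one, compliance is still a post-randomisation variable that refers to different programmes and does not belong with baseline characteristics.

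This affects one of five named factors in a specific objective. The main between-arm comparison is not undermined. The rank results rest on 8E being complete as written. The 18% to 81% range rests on assumed correlations of 0.2 to 0.5, n = 30 and a two-sided test. The 71% assumes a diary kept from day 1 to day 97.

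**What to change.** 1. In section 5.1 and SAP item e, take compliance out of the characteristics analysed for influence on the effect of the intervention.
2. In section 1, restate the adherence part of the specific objective as an exploratory association within the intervention arm, not as a modifier of effectiveness. Name the analysis in the SAP, for instance under item g, and say that the association may reflect recovery.
3. In section 4, compute adherence up to each outcome visit and use only that figure for that visit's outcomes.
4. In section 8E, state whether controls keep a diary. If they do not, say that the trial compares the whole package, diary monitoring included, with usual guidelines.

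The cost is a few sentences, and the adherence objective becomes exploratory. An equivalent diary for controls is optional. It would balance the reminder at the price of one printed diary per control, but it may change usual care, and it would not make adherence a valid moderator.

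### Complications are recorded only as they surface, with no question common to both arms, while physiotherapy sessions are specified for one arm only, so recorded harms are at risk of detection bias

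*Combined protocol and SAP*

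**What the plan says.** The instruction on recording harms is in the closing paragraph of section 8 (Study sequence): "All complications will be documented by the principal investigator. No adverse effects are expected". The same paragraph sends subjects whose modified Harris or VAS score has worsened at week 4, or who show surgical complications, back to their traumatologist, who decides whether they stay in the programme.

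Complications are not among the dependent variables in 5.2, which are ROM, orthopedic tests, VAS and modified Harris. They are not in the evaluation sequence of 8B, which 8F and 8G repeat, and the SAP does not analyse them.

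Contacts specified after surgery:

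- **Both arms:** a traumatologist visit (8D), "in addition to a follow-up visit by the traumatologist after two weeks of the intervention", read here as two weeks after the arthroscopy. The evaluation "is repeated 4 weeks after surgery to subjects of both groups" (8F), and again at 14 weeks (8G). Section 7 gives the same timing: "Data will be recorded at three times: before surgery, after 4 weeks and after 14 weeks of surgery".
- **Intervention arm:** "a physiotherapy session of 45 minutes each one every two weeks for a total of 7 sessions" (8E), at weeks 2, 4, 6, 8, 10, 12 and 14, plus a home exercise diary.
- **Control arm:** "The subjects of the control group follow the general postsurgical treatment protocol described by Gocen et al" (8E). The number of supervised sessions is not given.

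Section 2 adds: "The interventionist physiotherapist will perform the randomization on the day of the first post-surgery physiotherapy session". That implies at least one session for controls, although section 8 places randomization (8C) before surgery.

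**The concern.** If nobody is told to ask about complications, they are recorded when a subject happens to mention one or a clinician happens to notice one. The chance of that depends on how often the subject is seen, and the plan specifies contact frequency differently by arm. Equal true harm could therefore appear as more complications under the new protocol. If the records are judged too uneven to use, the trial would instead report on effectiveness with no usable harm comparison. Analysis cannot recover events that were never recorded.

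The referral rule is also touched. Its complication trigger, unlike its Harris/VAS trigger, is not tied to week 4. Earlier noticing in one arm could lead to more reviews, and possibly more departures from the programme, in that arm.

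Section 2 also asks subjects not to disclose their group to, or consult with, the surgeon or the evaluator. This may be meant to cover allocation only. But those are the only post-surgery contacts clearly scheduled for controls, so without an explicit question spontaneous reporting there may be discouraged.

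**Working it through.** **Inputs.** Contact weeks from section 8 (D to G); about 30 subjects per group from the SAP (Size Sample and Feasibility). The documents give no complication rate, event duration or number of control sessions, so these are assumptions below.

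**1. The plan's own figure.** Sessions every two weeks from week 2 to week 14: (14 − 2)/2 + 1 = 7. This agrees with 8E.

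**2. Contact weeks, assuming no control sessions beyond the shared contacts.**
- Intervention: 2, 4, 6, 8, 10, 12, 14 (7 distinct weeks; longest gap 2 weeks).
- Control: 2, 4, 14 (3 distinct weeks; longest gap 14 − 4 = 10 weeks).
- Intervention-only: 6, 8, 10, 12 (4 weeks).

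**3. Illustrative detection model.** Assume equal true rates, onset uniform over weeks 0 to 14, and an event recorded only if it is present at a contact, with no later recall. With certain detection at each contact, the proportion recorded is the share of onset times for which a contact falls within the event's duration. For 2-week events, control onsets caught are weeks 0–2, 2–4 and 12–14, or 6/14. For 4-week events they are weeks 0–4 and 10–14, or 8/14. With detection probability q per contact, the proportion is the average over onset of 1 − (1 − q)^k, where k is the number of contacts during the event.

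| Event duration | Intervention (q = 1) | Control (q = 1) | Ratio, q = 1 | Ratio, q = 0.5 |
|---|---|---|---|---|
| 1 week | 7/14 = 50.0% | 3/14 = 21.4% | 2.33 | 2.33 |
| 2 weeks | 100% | 6/14 = 42.9% | 2.33 | 2.33 |
| 4 weeks | 100% | 8/14 = 57.1% | 1.75 | 2.22 |
| 8 weeks | 100% | 12/14 = 85.7% | 1.17 | 1.81 |
| to week 14 | 100% | 100% | 1.00 | 1.46 |

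With an assumed true rate of 10% in both arms and 2-week events, recorded rates would be 10.0% and 0.10 × 0.429 = 4.3%, or about 3 and 1.3 events at 30 per arm.

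**4. Sensitivity to control sessions.** One control session near week 2 adds no new contact week and leaves the q = 1 ratios unchanged. Later control sessions shrink them. If controls were seen in the same weeks as the intervention arm, and equally often, every ratio would be 1.0.

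**5. What zero recorded events would show.** The one-sided 95% upper bound is 1 − 0.05^(1/n): 9.5% for n = 30 and 4.9% for n = 60. The two-sided version, 1 − 0.025^(1/n), gives 11.6% and 6.0%. A true 5% rate would give no events in an arm of 30 with probability 0.95^30 = 0.215.

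**The case against.** Several stronger readings are tempting, and the documents do not support them.

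- **That the control arm has no sessions.** The plan defines control care only by a cited protocol and does not state how many sessions it contains. Section 2 implies at least one. Every ratio above other than 1.0 depends on the assumption that there are no later ones.
- **That the intervention arm has seven extra contacts.** Three of the seven sessions fall in weeks when both arms are seen anyway. At most four weeks are intervention-only. A shared contact schedule exists; what it lacks is a question about complications.
- **That any harm comparison must be biased.** The bias is a risk, and its size depends on event duration. It is near nil for events that persist to week 14 and are reliably asked about.
- **That the plan will conclude there is no harm, or contradicts itself.** The SAP plans no between-arm harm comparison, and the closing sentence states an expectation. It can be read as referring to the physiotherapy, while the referral rule refers to complications of surgery.
- **That the whole referral rule is compromised.** The Harris/VAS trigger is assessed at week 4 in both arms by a blinded evaluator. Only the complication trigger, mainly after week 4, is exposed.

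Two further objections stand. The model allows no recall while the remedy relies on recall, so to the extent that subjects remember and report earlier events, 2.33 and 1.75 overstate the bias. And asking about complications at week 4 could reveal allocation to the evaluator who measures outcomes again at week 14; the remedy has to deal with that.

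None of this removes the core point: no method of asking is stated, and the opportunity to be noticed is specified differently by arm.

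**Conclusion.** The concern holds in limited form. The plan provides no standard ascertainment of complications that is equal by arm, and it specifies physiotherapist contact for the intervention arm only. If controls have no sessions after the early postoperative period, recorded complications and the later referrals they trigger are at risk of detection bias. The illustrative ratio runs from 1.0 to 2.33 with certain detection at each contact. It rests on no control sessions, no recall, uniform onset and equal true rates, so it shows the possible scale and is not an estimate.

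Equal ascertainment would make the arms comparable but would not support a conclusion of no harm; at about 30 per arm the limit there is sample size. The change is worth making because it is cheap and the data cannot be recovered afterwards.

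**What to change.** - Put the same fixed complication question to both arms at the existing evaluations, after the outcome measurements: since surgery at week 4, since the last evaluation at week 14.
- Protect blinding. Use a short self-completed form returned to someone other than the blinded evaluator, or a script that forbids mention of sessions or allocation.
- Add complications to 5.2. In the SAP, report them descriptively by allocated group from these common-contact reports only. List events first reported at physiotherapy sessions or in the diary separately.
- State the control-arm contacts in section 8E.
- Replace the closing expectation in section 8 with a statement that observed complications will be reported by arm, and draw no conclusion of no harm from few or zero events.

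**Cost:** one question at two existing visits and one descriptive table, with no added visit and no change to treatment. Recall will be imperfect, though the same question and recall periods apply to both arms. A little visit time is used, and a small unblinding risk remains, which the form or script limits.
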